11.1.2 Progression-Free Survival

Overall Survival: Overall Survival (OS) is defined as the time from time of registration to death due to any cause, or censored at date last known alive. We will evaluate for survival differences among patients that respond based on transplant status.

Progression-Free Survival: Progression-Free Survival (PFS) is defined as the time from time of registration to the earlier of progression or death due to any cause. Participants alive without disease progression are censored at date of last disease evaluation.

12. STUDY OVERSIGHT AND DATA REPORTING / REGULATORY REQUIREMENTS

Adverse event lists, guidelines, and instructions for AE reporting can be found in [Section 7.0](#) (Adverse Events: List and Reporting Requirements).

12.1 Study Oversight

This protocol is monitored at several levels, as described in this section. The Protocol Principal Investigator is responsible for monitoring the conduct and progress of the clinical trial, including the ongoing review of accrual, patient-specific clinical and laboratory data, and routine and serious adverse events; reporting of expedited adverse events; and accumulation of reported adverse events from other trials testing the same drug(s). The Protocol Principal Investigator and statistician have access to the data at all times through the CTMS web-based reporting portal.

For Phase 1 studies, all decisions regarding dose escalation/expansion/de-escalation require sign-off by the Protocol Principal Investigator through the CTMS/IWRS. In addition, for the Phase 1 portion, the Protocol Principal Investigator will have at least monthly, or more frequently, conference calls with the Study Investigators and the CTEP Medical Officer(s) to review accrual, progress, and adverse events and unanticipated problems.

All Study Investigators at participating sites who register/enroll patients on a given protocol are responsible for timely submission of data via Medidata Rave and timely reporting of adverse events for that particular study. This includes timely review of data collected on the electronic CRFs submitted via Medidata Rave.

All studies are also reviewed in accordance with the enrolling institution's data safety monitoring plan.

In addition to reporting to NCI/ETCN, it is mandatory for all participating sites to report all grade 4 events within 24 hours if possible, no more than 72 hours, to the Overall Study Chair except for those mentioned in section 7.3.4. All grade 5 events should be reported to the Overall Study Chair within 24 hours.

12.2 Data Reporting

Data collection for this study will be done exclusively through Medidata Rave. Access to the trial in Rave is granted through the iMedidata application to all persons with the appropriate roles assigned in the Regulatory Support System (RSS). To access Rave via iMedidata, the site user must have an active CTEP IAM account (check at <<https://ctepcore.nci.nih.gov/iam>>) and the appropriate Rave role (Rave CRA, Read-Only, Rave CRA (Lab Admin), Rave SLA, or Rave Investigator) on either the LPO or participating organization roster at the enrolling site. To hold the Rave CRA role or Rave CRA (Lab Admin) role, the user must hold a minimum of an AP registration type. To hold the Rave Investigator role, the individual must be registered as an NPIVR or IVR. Associates can hold read-only roles in Rave.

Upon initial site registration approval for the study in RSS, all persons with Rave roles assigned on the appropriate roster will be sent a study invitation e-mail from iMedidata. To accept the invitation, site users must log into the Select Login (<https://login.imedidata.com/selectlogin>) using their CTEP-IAM user name and password, and click on the "accept" link in the upper right-corner of the iMedidata page. Please note, site users will not be able to access the study in Rave until all required Medidata and study specific trainings are completed. Trainings will be in

the form of electronic learnings (eLearnings), and can be accessed by clicking on the link in the upper right pane of the iMedidata screen.

Users that have not previously activated their iMedidata/Rave account at the time of initial site registration approval for the study in RSS will also receive a separate invitation from iMedidata to activate their account. Account activation instructions are located on the CTSU website, Rave tab under the Rave resource materials (Medidata Account Activation and Study Invitation Acceptance). Additional information on iMedidata/Rave is available on the CTSU members' website under the Rave tab or by contacting the CTSU Help Desk at [name] or by e-mail at [contact].

12.2.1 Method

This study will be monitored by the Clinical Trials Monitoring Service (CTMS). Data will be submitted to CTMS at least once every two weeks via Medidata Rave (or other modality if approved by CTEP). Information on CTMS reporting is available at <http://www.theradex.com/clinicalTechnologies/?National-Cancer-Institute-NCI-11>. On-site audits will be conducted three times annually (one annual site visit and two data audits). For CTMS monitored studies, after users have activated their accounts, please contact the Theradex Help Desk at [contact] or by email at [contact] for additional support with Rave and completion of CRFs.

12.2.2 Responsibility for Data Submission

For ETCTN trials, it is the responsibility of the PI(s) at the site to ensure that all investigators at the ETCTN Sites understand the procedures for data submission for each ETCTN protocol and that protocol specified data are submitted accurately and in a timely manner to the CTMS via the electronic data capture system, Medidata Rave.

Data are to be submitted via Medidata Rave to CTMS on a real-time basis, but no less than once every 2 weeks. The timeliness of data submissions and timeliness in resolving data queries will be tracked by CTMS. Metrics for timeliness will be followed and assessed on a quarterly basis. For the purpose of Institutional Performance Monitoring, data will be considered delinquent if it is greater than 4 weeks past due.

Data from Medidata Rave and CTEP-AERS is reviewed by the CTMS on an ongoing basis as data is received. Queries will be issued by CTMS directly within Rave. The queries will appear on the Task Summary Tab within Rave for the CRA at the ETCTN to resolve. Monthly web-based reports are posted for review by the Drug Monitors in the IDB, CTEP. Onsite audits will be conducted by the CTMS to ensure compliance with regulatory requirements, GCP, and NCI policies and procedures with the overarching goal of ensuring the integrity of data generated from NCI-sponsored clinical trials, as described in the ETCTN Program Guidelines, which may be found on the CTEP (http://ctep.cancer.gov/protocolDevelopment/electronic_applications/adverse_events.htm) and CTSU websites.

An End of Study CRF is to be completed by the PI, and is to include a summary of study endpoints not otherwise captured in the database, such as (for phase 1 trials) the recommended phase 2 dose (RP2D), and a description of any dose-limiting toxicities (DLTs). CTMS will utilize a core set of eCRFs that are Cancer Data Standards Registry and Repository (caDSR) compliant (<http://cbiit.nci.nih.gov/ncip/biomedical-informatics-resources/interoperability-and-semantics/metadata-and-models>). Customized eCRFs will be included when appropriate to meet unique study requirements. The PI is encouraged to review the eCRFs, working closely with CTMS to ensure prospectively that all required items are appropriately captured in the eCRFs prior to study activation. CTMS will prepare the eCRFs with built-in edit checks to the extent possible to promote data integrity.

CDUS data submissions for ETCTN trials activated after March 1, 2014, will be carried out by the CTMS contractor, Theradex. CDUS submissions are performed by Theradex on a monthly basis. The trial's lead institution is responsible for timely submission to CTMS via Rave, as above.

Further information on data submission procedures can be found in the ETCTN Program Guidelines (http://ctep.cancer.gov/protocolDevelopment/electronic_applications/adverse_events.htm).

12.3 CTEP Multicenter Guidelines

N/A

12.4 Collaborative Agreements Language

The agent(s) supplied by CTEP, DCTD, NCI used in this protocol is/are provided to the NCI under a Collaborative Agreement (CRADA, CTA, CSA) between the Pharmaceutical Company(ies) (hereinafter referred to as "Collaborator(s)") and the NCI Division of Cancer Treatment and Diagnosis. Therefore, the following obligations/guidelines, in addition to the provisions in the "Intellectual Property Option to Collaborator" (http://ctep.cancer.gov/industryCollaborations2/intellectual_property.htm) contained within the terms of award, apply to the use of the Agent(s) in this study:

1. Agent(s) may not be used for any purpose outside the scope of this protocol, nor can Agent(s) be transferred or licensed to any party not participating in the clinical study. Collaborator(s) data for Agent(s) are confidential and proprietary to Collaborator(s) and shall be maintained as such by the investigators. The protocol documents for studies utilizing Agents contain confidential information and should not be shared or distributed without the permission of the NCI. If a copy of this protocol is requested by a patient or patient's family member participating on the study, the individual should sign a confidentiality agreement. A suitable model agreement can be downloaded from: <http://ctep.cancer.gov>.

2. For a clinical protocol where there is an investigational Agent used in combination with (an)other Agent(s), each the subject of different Collaborative Agreements, the access to and use of data by each Collaborator shall be as follows (data pertaining to such combination use shall hereinafter be referred to as "Multi-Party Data"):
 - a. NCI will provide all Collaborators with prior written notice regarding the existence and nature of any agreements governing their collaboration with NCI, the design of the proposed combination protocol, and the existence of any obligations that would tend to restrict NCI's participation in the proposed combination protocol.
 - b. Each Collaborator shall agree to permit use of the Multi-Party Data from the clinical trial by any other Collaborator solely to the extent necessary to allow said other Collaborator to develop, obtain regulatory approval or commercialize its own Agent.
 - c. Any Collaborator having the right to use the Multi-Party Data from these trials must agree in writing prior to the commencement of the trials that it will use the Multi-Party Data solely for development, regulatory approval, and commercialization of its own Agent.
3. Clinical Trial Data and Results and Raw Data developed under a Collaborative Agreement will be made available to Collaborator(s), the NCI, and the FDA, as appropriate and unless additional disclosure is required by law or court order as described in the IP Option to Collaborator (http://ctep.cancer.gov/industryCollaborations2/intellectual_property.htm). Additionally, all Clinical Data and Results and Raw Data will be collected, used and disclosed consistent with all applicable federal statutes and regulations for the protection of human subjects, including, if applicable, the *Standards for Privacy of Individually Identifiable Health Information* set forth in 45 C.F.R. Part 164.
4. When a Collaborator wishes to initiate a data request, the request should first be sent to the NCI, who will then notify the appropriate investigators (Group Chair for Cooperative Group studies, or PI for other studies) of Collaborator's wish to contact them.
5. Any data provided to Collaborator(s) for Phase 3 studies must be in accordance with the guidelines and policies of the responsible Data Monitoring Committee (DMC), if there is a DMC for this clinical trial.
6. Any manuscripts reporting the results of this clinical trial must be provided to CTEP by the Group office for Cooperative Group studies or by the principal investigator for non-Cooperative Group studies for immediate delivery to Collaborator(s) for advisory review and comment prior to submission for publication. Collaborator(s) will have 30 days from the date of receipt for review. Collaborator shall have the right to request that publication be delayed for up to an additional 30 days in order to ensure that Collaborator's confidential and proprietary data, in addition to Collaborator(s)'s intellectual property rights, are protected. Copies of abstracts must be provided to CTEP for forwarding to Collaborator(s) for courtesy review as soon as possible and preferably at least three (3) days prior to submission, but in any case, prior to presentation at the meeting or publication in the proceedings. Press

releases and other media presentations must also be forwarded to CTEP prior to release. Copies of any manuscript, abstract and/or press release/ media presentation should be sent to:

Email: [contact]

The Regulatory Affairs Branch will then distribute them to Collaborator(s). No publication, manuscript or other form of public disclosure shall contain any of Collaborator's confidential/ proprietary information.

12.5 Genomic Data Sharing Plan

Correlative studies proposed will aim to include genotyping patient leukemic blasts. If genomic data will be studied, analyzed, and collected, then we will plan to share and store this data in an NIH/NCI Genomic Data Biorepository (e.g., dbGaP, Cancer Genomic Database, other) following the genomic data sharing policy.

13. STATISTICAL CONSIDERATIONS

13.1 Study Design/Endpoints

This is an open-label phase 1 study using a standard 3+3 dose-escalation design with planned dose escalation of ipilimumab in combination with decitabine, to define the safety profile and MTD (RP2D) in patients with R/R MDSAML with and without previous allogeneic HSCT. Two arms are planned. Arm A will include a cohort of patients who are post-transplant (patients who were transplanted by allogeneic HSCT at any time). Arm B will include a cohort of patients who are transplant naive (patients who never received allo-HSCT). Both cohorts will be tested at three different ipilimumab dose levels (dose level 0 (starting dose; first dose level): 3 mg/kg, dose level 1: 5 mg/kg, and dose level 2: 10 mg/kg). Three to six patients will be evaluated at each dose level per arm.

Please see section 5.1 for details on patient enrollment. We will demonstrate safety in the first dose level in patients on Arm B prior to enrolling patients onto Arm A. After safety is demonstrated at this first dose level, enrollment can then occur simultaneously without further delay or observation period. A dose de-escalation level (-1) will be allowed with ipilimumab at 1 mg/kg. Arm A does not need to complete dose escalation before Arm B if Arm B is able to move to dose-expansion; and vice versa. In the event that 0 of 3 patients in a dose level experience a DLT, the dose level may still be expanded to 6 evaluable patients based on observed toxicity at the current dose level at the discretion of the overall PI to capture patient safety prior to expanding.

Dose escalation will follow a standard 3+3 design exploring 3 dose levels of ipilimumab (starting at dose level 0, at 3 mg/kg) with decitabine (20 mg/m² daily x 5 consecutive doses). We will escalate to next dose cohort if 0/3 or 1/6 participants have a DLT during the first two cycles of combination therapy (cycles 1+2; first 8 weeks of combination therapy). If the rate of dose limiting toxicity (DLT) exceeds 30%, it is less likely that the dose of ipilimumab will be

dose-escalated. The table below provides the probability that the dose will be escalated, i.e., that 0 in 3 or 1 in 6 patients experience a DLT, given the true but unknown rate of DLT.

	True but unknown probability of DLT				
	0.10	0.20	0.30	0.40	0.50
P(escalate)	0.91	0.71	0.49	0.31	0.17

The MTD will be the highest dose at which 1 or fewer of 6 patients experience a DLT. If no MTD has been established, then dose level 2 will be used in the dose expansion cohort as the recommended phase 2 dose (RP2D). Once an MTD (or RP2D) has been established an expansion cohort will be enrolled for each arm. For a given arm, if all 3 dose cohorts are filled to 6 patients, then a 6 patient expansion will be added. If 2 or fewer dose cohorts are filled to 6 patients, then a 12 patient expansion will be added so that no more than 24 patients (dose escalation + expansion) will be treated on a given arm. Patients will be monitored for DLTs during the first 8 weeks of combination therapy (56 days from start of combination) during the induction phase only. If a patient experiences disease progression in cycle 1, the patient will be evaluable for DLT if the patient completes a minimum of 28 days. Any patient who does not complete cycle 1 for any reason other than DLT will be considered non-evaluable for dose escalation decisions and will be replaced by an additional patient at that same dose level. Patients in cycle 2 will be assessed for DLT.

Safety and tolerability of decitabine plus ipilimumab will be evaluated by means of drug related DLT (defined as first 8 weeks of combination treatment with decitabine and ipilimumab), AE reports (following CTCAE V.5 criteria), physical examinations, and laboratory safety evaluations. These results will be tabulated overall and by dose level to examine their frequency, organ systems affected, severity, and relationship to study drugs.

The goal of the expansion cohort will be to further assess the tolerability of decitabine plus ipilimumab. Frequency of grade 3 or higher non-hematologic toxicities will be reported by arm and frequency of all grade immune-related adverse events will be reported by arm. Additionally, GVHD for the patients on the post-transplant arm will be estimated and reported with a 90% exact binomial confidence interval.

Additionally, efficacy of decitabine plus ipilimumab will be assessed for the total number of patients enrolled at the MTD/RP2D for each arm. Anti-leukemic activity will be described in terms of best overall response rate (for AML, to include CR+CRI; for MDS, to include CR+marrow CR+PR+HI). Assuming 6 patients are enrolled at the MTD/RP2D from the dose escalation phase and an additional 6 patients for the cohort expansion, the 90% exact binomial confidence interval will be within +/- 25%. Assuming 6 patients are enrolled at the MTD/RP2D from the dose escalation phase and an additional 12 patients from the cohort expansion, the 90% exact binomial confidence interval will be within +/- 21%.

Overall survival (OS) is defined as the time from registration to death due to any cause or censored at the date last known alive. Progression-free survival (PFS) is defined as the time from registration to the earlier of progression or death due to any cause. Survival outcomes will be

estimated by the method of Kaplan and Meier. OS and PFS will be evaluated within each arm.

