Management and dose delays associated with the above adverse events are outlined in [Section 6](#).

Dose escalation will proceed within each cohort according to the following scheme. Dose-limiting toxicity (DLT) is defined above.

For patients who are removed from treatment because of a > 4 week delay in receiving the next dose of ipilimumab: this will be classified as a DLT only if AE resulting in the treatment delay qualifies as a DLT.

Number of Patients with DLT at a Given Dose Level	Escalation Decision Rule
0 out of 3	Enter 3 patients at the next dose level.
1 out of 3	Enter at least 3 more patients at this dose level. 
 • If 0 of these 3 patients experience DLT, proceed to the next dose level. • If 1 or more of this group experience DLT, then dose escalation is stopped, and this dose is declared the maximally administered dose. Three (3) additional patients will be entered at the next lowest dose level if only 3 patients were treated previously at that dose.
≥ 2	Dose escalation will be stopped. This dose level will be declared the maximally administered dose (highest dose administered). Three (3) additional patients will be entered at the next lowest dose level if only 3 patients were treated previously at that dose.
≤ 1 out of 6 at highest dose level below the maximally administered dose	This is generally the recommended phase 2 dose. At least 6 patients must be entered at the recommended phase 2 dose.

Delayed toxicities (toxicities after 8 weeks of combination therapy): As delayed toxicity may occur (immune related AE) at any point after checkpoint blockade therapy, we recommend that any event beyond the first 8 weeks of combination therapy that is considered to be an immune related AE or concerning for GVHD be reported to the Overall PI. These events will be captured and reported, but will not determine dose-escalation. These patients would also be removed from study if they have a toxicity event described in [section 5.2](#).

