5.3 Dose Expansion Cohorts

Once the RP2D is reached, an additional 6-12 patients will be treated at this dose per arm. For a given arm, if all 3 dose cohorts are filled to 6 patients, then a 6 patient expansion will be added. If 2 or fewer dose cohorts are filled to 6 patients, then a 12 patient expansion will be added so that no more than 24 patients (dose escalation + expansion) will be treated on a given arm.

For the expansion cohort, patients will continue to be monitored for occurrence of DLT. If ≥ 2 of 6 patients experience DLT, the Principal Investigator will discuss with all study investigators and with CTEP whether further addition of patients is needed to re-assess the RP2D. Monitoring of all safety and toxicity data is done by the Principal Investigator and the Corresponding Organization on a real-time basis as data are entered into Medidata Rave using the Web Reporting Module. All participating sites are expected to notify the Principal Investigator when a DLT has occurred.

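### The expansion rule does not keep each arm to 24 patients: with two dose levels at 6 and the third at 3, 15 + 12 = 27

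*Combined protocol and SAP*

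**What the plan says.** Section 13.1 sets out three ipilimumab levels (0, 1 and 2) in each arm: "Both cohorts will be tested at three different ipilimumab dose levels". "Three to six patients will be evaluated at each dose level per arm". A level with no dose-limiting toxicity (DLT) in its first 3 patients may be topped up at the overall PI's discretion: "the dose level may still be expanded to 6 evaluable patients based on observed toxicity".

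The escalation table in section 5.2 moves up after 0/3 or 1/6 DLTs. When a level is stopped, three "additional patients will be entered at the next lowest dose level if only 3 patients were treated previously at that dose". For the recommended phase 2 dose (RP2D), "At least 6 patients must be entered at the recommended phase 2 dose".

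Section 5.3 opens with a range: "Once the RP2D is reached, an additional 6-12 patients will be treated at this dose per arm". Sections 5.3 and 13.1 then give the same rule: 6 more patients if all three levels are filled to 6, but "If 2 or fewer dose cohorts are filled to 6 patients, then a 12 patient expansion will be added". The stated purpose is a ceiling: "then a 12 patient expansion will be added so that no more than 24 patients (dose escalation + expansion) will be treated" on an arm.

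Section 13.1 gives the precision of the response rate for 6 + 6 and 6 + 12 patients at the RP2D (90% exact intervals within 25 and 21 points). Section 13.2 assumes that every cohort is filled, states at most 24 patients per arm and at most 48 in total, and gives an enrolment table that sums to 48.

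**The concern.** The rule depends only on the number of levels at 6. It ignores whether the remaining level was opened. Two levels at 6 can mean 12 escalation patients (third level never opened) or 15 (third level opened and left at 3). The rule gives 12 more in both cases, and only the first case respects the ceiling.

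On the second kind of path the two halves of one sentence cannot both be followed. If the 12 is followed, the arm exceeds the stated maximum, and so can the study. If the ceiling is followed, the expansion is 9, a size the rule does not offer. The RP2D group is then normally 6 + 9 = 15, for which section 13.1 gives no precision.

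**Working it through.** **Inputs.** Three levels with 3 or 6 patients each (13.1); the escalation table (5.2); expansion of 6 if three levels hold 6, otherwise 12 (5.3, 13.1); cap of 24 per arm (5.3, 13.1) and 48 in total (13.2). Section 13.1 treats the expansion as additional to the escalation patients, so the two numbers add.

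**Reading of the escalation rule.** P(escalate) = (1−p)³ + 3p(1−p)⁵ gives 0.906, 0.709, 0.494, 0.309 and 0.172 for p = 0.10 to 0.50. This matches the plan's 0.91, 0.71, 0.49, 0.31 and 0.17.

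**The plan's 24.** With all cohorts filled, 6 + 6 + 6 = 18 and 18 + 6 = 24, as in section 13.2.

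**All configurations that end with an RP2D at levels 0 to 2:**

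| Levels 0/1/2 | Escalation | Levels at 6 | Expansion | Arm total |
|---|---|---|---|---|
| 6/6/6 | 18 | 3 | 6 | 24 |
| 3/3/6 or 3/6/3 | 12 | 1 | 12 | 24 |
| 6/6/not opened | 12 | 2 | 12 | 24 |
| 6/3/not opened | 9 | 1 | 12 | 21 |
| 3/3/3 * | 9 | 0 | 12 | 21 |
| 6/3/3 * | 12 | 1 | 12 | 24 |
| **3/6/6, 6/3/6 or 6/6/3** | **15** | **2** | **12** | **27** |

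\* Only if a level 2 with 0/3 goes straight to expansion.

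Only the last row breaks the cap, by 27 − 24 = 3. For the study: 27 + 24 = 51 if one arm overruns and the other reaches 24, and 2 × 27 = 54 if both overrun. A simple example is 0/3 at level 0, 1/6 at level 1 and 1/6 at level 2.

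**How often.** The documents give no DLT rate by dose, so the curves are my assumption, using rates from the plan's table. Worked case: 0.10/0.20/0.30, no early filling, and a 0/3 level 2 filled to 6.

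- Level 0: P(0/3) = 0.729; P(1/3 then 0/3) = 0.243 × 0.729 = 0.1771.
- Level 1: P(0/3) = 0.512; P(1/3 then 0/3) = 0.384 × 0.512 = 0.1966.
- Level 2: P(at least 2 of the first 3) = 0.216; otherwise it is filled to 6 (0.784), passing with 0.4202 and failing with 0.3638.
- 3/6/6: 0.729 × 0.1966 × 0.784 + 0.729 × 0.512 × 0.3638 × 0.896 = 0.234 (0.896 = level 1 still acceptable when topped up).
- 6/3/6: 0.1771 × 0.512 × 0.4202 = 0.038.
- 6/6/3: 0.1771 × 0.1966 × 0.216 + 0.1771 × 0.512 × 0.216 + 0.729 × 0.512 × 0.216 × 0.104 × 0.972 = 0.035 (last term: level 1 fails on top-up, 0.104, and level 0 holds, 0.972).
- Sum: 0.307.

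The same enumeration for other curves gives, per arm:

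| DLT rates, levels 0/1/2 | A | B | C |
|---|---|---|---|
| 0.10/0.10/0.10 | 0.289 | 0.116 | 0.022 |
| 0.10/0.20/0.30 | 0.307 | 0.221 | 0.125 |
| 0.20/0.20/0.20 | 0.230 | 0.139 | 0.045 |
| 0.20/0.30/0.40 | 0.169 | 0.139 | 0.097 |
| 0.30/0.40/0.50 | 0.072 | 0.065 | 0.049 |
| 0.10/0.30/0.50 | 0.208 | 0.182 | 0.186 |

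A: as in the worked case. B: no early filling, and a 0/3 level 2 goes straight to expansion. C: every 0/3 level is filled to 6. If the arms are independent and on the same curve, both overrun with the square of these values: 0.005–0.095 (A), 0.004–0.049 (B), 0.0005–0.035 (C).

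**Precision.** The largest half-width of the exact 90% interval is 0.2547 for n = 12 and 0.2088 for n = 18, which match the plan's 25 and 21 points to rounding. For n = 15 it is 0.2281. The largest distance from the estimate to a limit is 0.2441 (at 10/15).

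**The case against.** The strongest reply is that the cap governs. It is stated without qualification in both sections, and the range of 6 to 12 in section 5.3 admits 9, so a sensible reader would expand by 9 and nobody plans to treat 27. That is probably the intent. However, no passage states 9 or says which clause prevails, and the explicit rule names 12 for exactly this case.

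Section 13.2 does condition its figure on all cohorts being filled, and 18 + 6 = 24 is right for that case. It then uses the result as a maximum. Under the written rule the fully filled case is not the maximum, because leaving one level at 3 yields more patients.

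Discretionary filling can turn 3/6/6 or 6/3/6 into 6/6/6 and restore 24. It is optional, it refers to the level currently under study, and it cannot help 6/6/3 when level 2 closed on two or more DLTs in 3.

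Two details stand. If a 0/3 level 2 in 6/6/3 goes straight to expansion, the cap gives 3 + 9 = 12 at the RP2D, not 15. Replaced patients and use of level −1 can also push an arm past 24, which the plan's own figure ignores too.

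**Conclusion.** The concern holds. The written rule gives 27 against a stated maximum of 24 in an affected arm, and 51 or 54 against 48 for the study. The arithmetic rests on the documents alone.

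The probabilities rest on assumed DLT curves: 0.07–0.31 per arm (A), 0.065–0.22 (B) and 0.02–0.19 (C). They show that the path is not remote. They are not forecasts, and a curve between the tabulated rates (0.10/0.15/0.25, as in A) gives about 0.34.

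The severity is minor. The overrun is 3 patients per arm, and the escalation and RP2D decisions come before the expansion and do not change. What fails is the sample-size ceiling and, if the ceiling is kept, the completeness of the precision statement.

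**What to change.** Preferred: in sections 5.3 and 13.1, define the expansion as 24 minus the patients treated in escalation, up to 12. This gives 6 after 18 escalation patients, 9 after 15, and 12 after 12 or fewer. State in the same place whether patients who were treated and then replaced count towards the 24. If they do, one such patient on a 6/6/6 path leaves 24 − 19 = 5, below the 6 that section 5.3 promises.

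Add to section 13.1 the precision for 15 patients at the RP2D: exact 90% interval with half-width at most about 23 points (largest distance from the estimate to a limit about 24 points), and say which measure is meant. The cost is one sentence in each of 5.3 and 13.1 and one added figure.

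Alternative: keep 12 and restate the maxima in 5.3, 13.1 and 13.2 as 27 per arm and 54 in total for levels 0 to 2. This also changes the enrolment table.
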